9.2.2 Secondary analysis

The primary outcome change of glycemic control after adjustment for potential confounders will be further analyzed by ANCOVA with additional control variables. A correlation analysis will be performed with the age, sex, comorbidities, and diabetes side effects as potential control variables.

The resulting p-values will be checked. If Pearson's correlation coefficient has a p-value $< .05$, the control variable will be used to conduct further ANCOVA. The additional

ANCOVA will include the study groups, HbA1c baseline, and the selected control variables.

The secondary outcome change of depression symptoms after adjustment for potential confounders will be further analyzed by ANCOVA with additional control variables. A correlation analysis will be performed with the age, sex, comorbidities, and diabetes side effects as potential control variables.

The resulting p-values will be checked. If Pearson's correlation coefficient has a p-value $<.05$, the control variable will be used to conduct further ANCOVA. The additional ANCOVA will include the study groups, BDI baseline, and the selected control variables.

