9.2 Analysis of Outcomes

9.2.1 primary analysis

The primary variable is the Hb A1c plasma level.

The primary endpoint is the difference between Hb A1c level at baseline and three months later.

The primary outcome is the change of Hb A1c, compared between the different treatment groups using an Analysis of Covariance (ANCOVA), the General Linear Modeling approach to compare the study groups. The HbA1c and BDI at baseline will serve as control variables. HbA1c and BDI values at baseline are the values obtained at

the first visit before the start of the intervention. If the HbA1c value at baseline is missing, the first HbA1c value obtained during the first subsequent visits will be used.

The following hypothesis will be tested:

$H_0: \mu_{CBT} = \mu_{control}$ versus $H_1: \mu_{CBT} \neq \mu_{control}$

Where μ_{CBT} and $\mu_{control}$ are the expected mean values of the differences in HbA1c values belonging to the CBT and the control groups. The hypothesis will be tested on a 2-sided p-value with alpha ≤ 0.05 level of significance. The results will be displayed by means of the p-value, standard deviation of unadjusted values, and 95%-confidence interval. For that, the assumption of homogeneity of regression slope will be examined by testing the interaction effect of the independent variable and the covariate.

The secondary variable is the BDI score.

The secondary endpoint is the difference between BDI at baseline and three months later.

The secondary outcome is the change of BDI compared between the different study groups using an Analysis of Covariance (ANCOVA), the General Linear Modeling approach to compare the study groups. The HbA1c and BDI at baseline will serve as control variables. HbA1c and BDI values at baseline are the values obtained at the first visit before the start of the intervention. For that, the assumption of homogeneity of regression slope will be examined by testing the interaction effect of the independent variable and the covariate.

The following hypothesis will be tested:

$H_0: \mu_{CBT} = \mu_{control}$ versus $H_1: \mu_{CBT} \neq \mu_{control}$

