10.1 Data Monitoring

The trial has a calculated sample size of 80. The intervention duration is short for two months. Accordingly, the study is expected to bear no to minimal risk. Thus, no data monitoring committee (DMC) will be needed.

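### The supportive adjusted ANCOVAs choose their extra covariates by a Pearson p < .05 screen on the trial's own data, so the adjusted model depends partly on sampling noise; a fixed covariate list would serve better

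*Combined protocol and SAP*

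**What the plan says.** Section 9.2.2 of the combined protocol and SAP plans one further ANCOVA for HbA1c change and one for BDI change, each meant to adjust for potential confounders. The candidates are the same for both: "A correlation analysis will be performed with the age, sex, comorbidities, and diabetes side effects as potential control variables". A candidate is kept on one condition: if its Pearson correlation is significant at the .05 level, "the control variable will be used to conduct further ANCOVA". The screen is run separately for each outcome.

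Beyond the screened terms, the HbA1c version of this "ANCOVA will include the study groups, HbA1c baseline, and the selected control variables", and the BDI version of this "ANCOVA will include the study groups, BDI baseline, and the selected control variables". Each therefore guarantees only study group and that outcome's own baseline.

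Section 9.2.1 works differently. For both main ANCOVAs it fixes the covariates in advance: "The HbA1c and BDI at baseline will serve as control variables".

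Two details are left open in 9.2.2. It does not say what the candidates are correlated with (the change, the follow-up value or study group). It also does not say whether comorbidities and diabetes side effects enter as counts or as types, although section 8.2.4 records both.

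**The concern.** Covariate adjustment in a randomised trial serves two purposes: it removes the effect of chance imbalance in prognostic factors, and it improves precision. Both depend on how prognostic a factor is, and neither depends on whether its correlation crosses a significance threshold in a sample of this size. A screen at p < .05 with about 80 patients has limited power for modest correlations and a fixed false-positive rate for useless covariates. It also looks at the marginal correlation, not at what a covariate adds once the baseline value is in the model.

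The content of the adjusted model is therefore not known until the data have been screened. At stake are the interpretability and precision of a supportive analysis, and its ability to deliver the adjustment it is named for.

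**Working it through.** **Inputs from the documents.** Threshold .05 and four candidates per outcome (section 9.2.2). Sample size: "The trial has a calculated sample size of 80" (section 10.1). About 100 patients met the criteria and agreed to take part (section 12.3), so n = 100 is the upper value. Treatment tests are two-sided at 0.05 (section 9.2.1).

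**Assumptions.** The candidates are correlated with the outcome. True correlations lie between 0.2 and 0.4. Each candidate is a single variable, and candidates are mutually independent. Allocation is 1:1, since no ratio is stated. For power, the true group difference is 0.6 SD.

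The plan gives no figure on this point to reproduce. The sample size of 80 comes without an effect size, SD or power. With 40 per arm it corresponds to 80% power for a standardised difference of about 0.63, so 0.6 SD is a reasonable illustration.

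**Step 1: the threshold as a correlation.** r_crit = t / √(t² + n − 2). At n = 80, t = 1.991 and r_crit = 0.220. At n = 100, t = 1.984 and r_crit = 0.197.

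**Step 2: chance that a real factor is left out.** By Fisher's z, P(kept) = 1 − Φ(1.96 − atanh(r)·√(n − 3)) + Φ(−1.96 − atanh(r)·√(n − 3)). For r = 0.2 and n = 80: atanh(0.2) = 0.2027, times √77 = 8.775, gives 1.779. Then 1 − Φ(0.181) = 0.428, and the last term is negligible.

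| True r | Kept, n = 80 | Left out | Kept, n = 100 | Left out |
|---|---|---|---|---|
| 0.20 | 0.428 | 57.2% | 0.515 | 48.5% |
| 0.25 | 0.611 | 38.9% | 0.711 | 28.9% |
| 0.30 | 0.775 | 22.5% | 0.862 | 13.8% |
| 0.40 | 0.961 | 3.9% | 0.987 | 1.3% |

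If all four are prognostic, the chance at n = 80 of losing at least one is 1 − 0.428⁴ = 97% at r = 0.2 and 1 − 0.775⁴ = 64% at r = 0.3.

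**Step 3: chance of a spurious pick.** With four independent null tests, 1 − 0.95⁴ = 18.5% per outcome. If comorbidities (five categories in section 8.2.4) and side effects (three) were screened as types, there would be 2 + 5 + 3 = 10 tests, and 1 − 0.95¹⁰ = 40%.

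**Step 4: consequence for the treatment estimate.** This used a simulation of 20,000 trials per scenario, n = 80, with the outcome's own baseline always in the model, as in section 9.2.2.

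| All four covariates at | Power, screened | Power, all four fixed | Difference |
|---|---|---|---|
| r = 0.20 | 83.5% | 86.7% | 3.2 points |
| r = 0.25 | 87.3% | 91.4% | 4.1 points |
| r = 0.30 | 92.4% | 95.8% | 3.4 points |

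- Type I error was 4.8% to 5.3% for the screened model and 4.8% to 5.2% for the fixed one.
- If none of the four is prognostic, the mean SE is 0.211 with all four fixed, against 0.2047 screened: 0.211 / 0.2047 = 1.03.
- If two have r = 0.3 and two are useless, the SEs are nearly equal: 0.1872 fixed and 0.1858 screened, or 0.8% larger when fixed.
- With four candidates there are 2⁴ = 16 possible models. With all four at r = 0.2 and no treatment effect, all 16 occurred and none in more than 10% of trials.

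**Step 5: the two sections side by side.** The main models in 9.2.1 contain group, baseline HbA1c and baseline BDI. The additional HbA1c model in 9.2.2 has no baseline BDI, and the additional BDI model has no baseline HbA1c. They are therefore not the main model plus extra covariates. A difference between a main and an adjusted estimate could come from the dropped baseline as well as from the added terms.

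**The case against.** The strongest case for leaving this alone is that the consequence is small. The analysis is supportive, the main ANCOVAs have fixed covariates, and randomisation removes confounding in expectation. A missed factor does limited damage: with r = 0.2 and an imbalance of 0.45 SD, the estimate shifts by 0.2 × 0.45 = 0.09 SD, against an SE of about √(2/40) = 0.22 SD. All of that stands, and it limits the point to a minor one.

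Three stronger readings are tempting and are not supported.

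- A reader might infer that real prognostic factors are usually left out. That holds only below the r at which selection reaches 50%: about 0.22 at n = 80 (1.96/8.775 = 0.223 on the z scale) and about 0.20 at n = 100. A factor with r = 0.4 is nearly always kept.
- A reader might infer false-positive inflation. The screened model alone holds its level. Error rises to between 7.1% and 8.2%, with four prognostic covariates, only if a significant result in either an own-baseline ANCOVA or the screened model were counted as success. The plan does not say that it would be.
- A reader might infer discretionary model choice. The candidates and the rule are stated in advance, and section 9 describes a statistician blinded to study groups. Different covariate sets for two different outcomes are not an error in themselves.

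It is also fair to object that the plan never says the screen is against the outcome. If it is against study group, the rule becomes a baseline-imbalance test that keeps each factor about 5% of the time whatever its prognostic value. The omission figures above would then be too mild.

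**Conclusion.** The concern holds as a minor but real weakness, confined to the supportive analyses in section 9.2.2. The screen does not reliably deliver the adjustment it is meant to give at assumed correlations of 0.2 to 0.3, and it admits useless terms in roughly one trial in five per outcome. The practical loss is a model whose content is not fixed in advance, and some power when all the candidates are prognostic. The precision advantage of a fixed set disappears when only some are prognostic and becomes a small cost when none is.

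The size rests on assumed correlations, independent candidates, 1:1 allocation, a 0.6 SD effect and screening against the outcome. The reading of the text does not: the unspecified correlate, the unspecified coding and the dropped baseline are visible in the plan itself.

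**What to change.** Replace the screen with one fixed adjusted ANCOVA per outcome: study group, baseline HbA1c, baseline BDI, age, sex, number of comorbidities and number of diabetes side effects, all kept whatever their p-values. State the coding of each. This makes the adjusted model the section 9.2.1 model plus four named terms, and it removes the question of what the candidates are correlated with.

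Section 12.3 says that the trial is already in data analysis, so timing matters. If the group comparison has not been unblinded, make and date the change before it is. If it has been seen, report the fixed model beside the screened one and label it post hoc.

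The cost is SAP wording and no new data, since all these variables are already collected. The statistical downside is an SE about 3% larger if none of the four covariates is prognostic. Restoring the other outcome's baseline uses one further degree of freedom relative to the section 9.2.2 models, which the main models already spend.

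### The further ANCOVAs in Section 9.2.2 each omit a baseline covariate that the Section 9.2.1 models include, so they are not the main models plus confounders

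*Combined protocol and SAP*

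**What the plan says.** Section 9.2.1 gives the main model for HbA1c change and states: "The HbA1c and BDI at baseline will serve as control variables". The same sentence is repeated for the secondary outcome, introduced by "The secondary outcome is the change of BDI compared between the different study groups using an Analysis of Covariance (ANCOVA". Both main models therefore contain study group, baseline HbA1c and baseline BDI.

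Section 9.2.2 says that each outcome, after adjustment for potential confounders, will be "further analyzed by ANCOVA with additional control variables". It then lists the terms:

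- For HbA1c change, the "ANCOVA will include the study groups, HbA1c baseline, and the selected control variables".
- For BDI change: "The additional ANCOVA will include the study groups, BDI baseline, and the selected control variables".

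The candidates are named for each outcome: "A correlation analysis will be performed with the age, sex, comorbidities, and diabetes side effects as potential control variables". A candidate enters only if its Pearson correlation has p<.05, in which case "the control variable will be used to conduct further ANCOVA". No reason is given for leaving out the other baseline value.

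**The concern.** The wording of Section 9.2.2 leads a reader to expect the main model with more terms. The term lists describe something else: one baseline covariate is taken out while others may be put in. An adjusted analysis of this kind is usually read next to the main result, to see whether the group effect changes once confounders are included. If the two estimates differ, the plan as written gives no way to tell whether the added variables or the missing baseline caused it. A baseline value that the plan itself chose to control, and that is already collected, is also left unused, with some loss of precision. Finally, the announced aim and the term lists support two different models, which leaves the analyst a choice.

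**Working it through.** **Step 1. Compare the terms** (Sections 9.2.1 and 9.2.2; k is the number of candidates selected).

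| Outcome | 9.2.1 | 9.2.2 as written | 9.2.2 with both baselines |
|---|---|---|---|
| HbA1c change | group, HbA1c, BDI | group, HbA1c, k selected | group, HbA1c, BDI, k selected |
| BDI change | group, HbA1c, BDI | group, BDI, k selected | group, HbA1c, BDI, k selected |
| Baseline covariates | 2 | 1 + k | 2 + k |

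The candidates are age, sex, comorbidities and diabetes side effects. Neither baseline score is among them, so for every k the 9.2.2 model lacks one term of the 9.2.1 model. It never contains the main model.

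**Step 2. Precision.** Let r be the partial correlation of the omitted baseline with the outcome, given the other terms. Leaving it out multiplies the standard error (SE) of the group effect by about 1/sqrt(1 − r²). The documents do not give r, so a range is shown:

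| Assumed r | 1/sqrt(1 − r²) − 1 |
|---|---|
| 0 | 0% |
| 0.1 | 1/sqrt(0.99) − 1 = 0.5% |
| 0.2 | 1/sqrt(0.96) − 1 = 2% |
| 0.3 | 1/sqrt(0.91) − 1 = 5% |
| 0.4 | 1/sqrt(0.84) − 1 = 9% |

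**Step 3. Chance imbalance.** If the arms differ by 0.2 SD on the omitted baseline, the estimate shifts by about 0.2 × r outcome SDs: 0.02 at r = 0.1 and 0.08 at r = 0.4. The direction is random, so the average shift under randomisation is zero.

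**Step 4. Simulation of the whole procedure.** The total of 80 patients is from Section 10.1. The rest is assumed: 40 per arm, four independent candidates unrelated to the outcome, screening against the outcome change at p<.05, slope 0.3 for the outcome's own baseline, and 4,000 trials. Only trials with at least one selected candidate are kept. Mean SE of the group effect, in outcome SDs:

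| Slope of omitted baseline | 9.2.1 | 9.2.2 as written | 9.2.2 with both baselines |
|---|---|---|---|
| 0.2 | 0.211 | 0.210 | 0.207 |
| 0.3 | 0.204 | 0.209 | 0.200 |

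At slope 0.3 the model as written has an SE 2.5% above the main model (0.209/0.204 = 1.025) and 4.5% above the repaired model (0.209/0.200 = 1.045). The second figure agrees with Step 2. At slope 0.2 there is no loss against the main model, and a loss of 1.4% against the repaired one (0.210/0.207 = 1.014).

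**Step 5. Movement of the estimate.** In the same trials at slope 0.3, the SD of the 9.2.2 estimate minus the 9.2.1 estimate was 0.087 outcome SDs as written and 0.054 with both baselines included. Restoring the baseline cuts that SD by 38% (1 − 0.054/0.087 = 0.38). The remaining movement comes from the data-driven screen.

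**The case against.** The strongest case against this point is that little depends on it. Section 9.2.2 is supportive, no decision in the documents rests on it, and the main tests of both outcomes already include both baselines. Group, own baseline and selected covariates form a legitimate model in its own right. The plan does not say in so many words that 9.2.2 tests the robustness of the main result. The partial correlation may also be small, since eligibility restricts BDI to the range from mild mood disturbance to moderate depression. All of this stands, and it limits the size of the point. It does not remove the mismatch, because the section itself describes its covariates as additional and then lists a set that omits one.

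Two stronger readings are tempting:

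- A reader might infer that the adjusted model will often have fewer covariates than the main one. By count, that happens only if no candidate is selected. The selection rule is conditional, and its natural reading is that no further ANCOVA is then run. With one selected the counts are equal, and with two or more the 9.2.2 model is larger. A probability for the empty case would also require the candidates to be independent and unrelated to the outcome, which the documents do not support.
- A reader might infer that every discrepancy between the two estimates comes from the missing baseline. Step 5 shows otherwise: much of it remains once the baseline is restored.

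**Conclusion.** The inconsistency is real and affects both outcomes. The 9.2.2 model is never the 9.2.1 model plus confounders, so a difference between the two estimates cannot be credited to the added variables alone. This follows from the text and needs no assumption.

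The size is modest, and every figure for it rests on assumed correlations or slopes. The documents do not support a claim that the main analyses are biased or invalid. Because 9.2.2 describes its covariates as additional, this may be a drafting omission. It is worth correcting because the correction is nearly free.

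**What to change.** In Section 9.2.2, define each additional ANCOVA, for HbA1c change and for BDI change, as the Section 9.2.1 model (study group, baseline HbA1c, baseline BDI) plus the additional control variables.

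The cost is SAP wording and one degree of freedom per model. No new data are needed, since 9.2.1 already requires both baseline values. Section 12.3 says the trial is in the data analysis phase, so the change should be documented before results by group are seen; if they have been seen, report both versions. The change leaves the p<.05 screen in place, so the comparison with the main result will be cleaner but not free of selection effects.

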9.2.3 Subgroup analysis

A subgroup analysis of the type of diabetes treatment will be conducted for the primary outcome. This will be done by including diabetes treatment type and study groups variables in the ANCOVA.

The HbA1c values for the subgroup analysis will be displayed by descriptive statistics (n, mean, standard deviation, median, and interquartile-range (IQA)) and they will be compared by p-values of t-test.

Descriptive statistics of demographic and baseline medical and psychosocial characteristics will be displayed by type of diabetes treatment. Exploratory p-values of t-test and chi-square tests will be presented to examine differences between both subgroups.

10 Monitoring

10.1 Data Monitoring

The trial has a calculated sample size of 80. The intervention duration is short for two months. Accordingly, the study is expected to bear no to minimal risk. Thus, no data monitoring committee (DMC) will be needed.

10.2 Harms

An adverse event is defined by this study as any unfavorable medical occurrence in a subject that has a temporal relationship to the study intervention (CBT). All adverse events will be collected and recorded after the patients will be enrolled in the study. However, only serious adverse events that result in severe or permanent disability or prolonged hospitalization will be reported to the Research Ethical Committee (REC).

There are no to minimal risks associated with the CBT program. The program targets depressive symptoms. However, like any medical treatment, the program may bear the risk that it will not work. In this case, patients may feel disappointed that their depression will deteriorate. However, such clinical deterioration is rare. (Morisky et al. 1986; Delgado & Lima 2011).

Potential side effects may include risks associated with blood withdrawal. There may be some minor discomfort or pain associated with collecting blood. Some participants may experience minor local bruising or brief lightheadedness. For that, blood specimens will be collected by trained and experienced lab technicians. Some patients might be slightly distressed by the rating scales. Thus, we will keep the collected information as minimal as possible and will be part of the clinical care.

Possible benefits of the program include reduced depressive symptoms, distress, and impairment, and clinically significant remission of depressive symptoms.

10.3 Auditing

Regular team meetings will be conducted to address any difficulties experienced during the study especially those participants may be having difficulties and ways of best dealing with them. Serious adverse events will be reported to the REC at the Faculty of Medicine, Cairo University.

11 Ethics and dissemination

11.1 Research Ethics Approval

The study protocol, consent form, participant education, and recruitment materials both in local language and English versions have been reviewed and approved on December 2018 before study implementation by the department of public health and community medicine; department of psychiatry; department of internal medicine at Elkasr Eleini Medical School, the REC at Cairo University; and the administrative office at Alagouza health district.

11.2 Protocol Amendment

Any modifications to the protocol which may impact the study conduct or may cause potential benefits or harm to the patient including changes of study objectives, design, procedure, target population, sample size, or significant administrative matters will require a formal amendment to the protocol. Such amendment will be agreed upon by the REC at Cairo University prior to implementation. Minor administrative changes of the protocol that have no effect on the study will only need the approval of the department of public health and community medicine and will be documented in a memorandum. The REC may be notified of such changes.

